7.3. REPORTING ADVERSE EVENTS AND DEATH

All adverse events will be assessed for the need for prompt reporting. We follow the guidelines set forth by the Emory IRB for reporting AEs. Any event that fulfills the following criteria being unanticipated (as defined in section 7.2), probably or possibly related to study participation (drug effect or as a consequence of a study procedure), and involving risk for participants or others is considered an unanticipated problem and will be reported to the Emory IRB within 10 days. If an event could be explained by the underlying medical condition, it is not considered related and hence not reportable. Any SAE as defined in **section 7.2** that does not fit all the criteria of being an unanticipated problem will be reported during continuing review. Deaths of participants during the study will be promptly reported to the IRB if related to study participation and reported during continuing review if they are not related to study participation.

7.4. FOLLOW-UP FOR ADVERSE EVENTS

All AE/SAE will be recorded in the participant chart with start/stop date. The study physician may perform additional evaluations, unscheduled visits, phone communication, repeat blood testing, or refer to the emergency room or the participant healthcare provider for medical care if necessary. If the event results in intervention discontinuation (>5 months) but not study withdrawal, the participant will be followed as defined in the study. They will also be invited to perform the final visit evaluation including all study procedures planned for that visit if the participant has been in the study for more than 5 months post-baseline evaluation.

When a subject notifies the study team that they have symptoms suggestive of a treatment-emergent AE/SAE, the study physician will review the incident and determine if the subject is safe to continue in the study. The physician may discontinue the study medication immediately, elect to lower the dose of the study medication, ask subject to present to the study center for a safety evaluation, and/or monitor the subject's concern. The subject may continue in the study if on the lower dose of the study medication, they experience some resolution of symptoms. In those on 20 mg and 40 mg, the doses will be decreased to the next lower dose. In those on 10 mg of Montelukast, a trial of every other day 10 mg of Montelukast will be attempted prior to discontinuation.

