5.3. CONCOMITANT INTERVENTION

5.3.1. ALLOWED INTERVENTIONS

Participants will continue to receive their usual care from their regular primary care physicians. In the event that during the trial period, a participant is required to be on a LTRA (Montelukast or other similar agents), the prescribing physician and the subject will be informed they might be receiving Montelukast to avoid any overlap. If an alternative treatment is prescribed that is safe to be used with Montelukast, then they can continue on the study medications. Participants who start on a LTRA (or a drug that potentially lead to contraindication for using LTRA) clinically will have their study medication discontinued but will continue to be in the study and have their subsequent visits and measures completed.

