8. INTERVENTION DISCONTINUATION AND STUDY WITHDRAWAL

A subject may choose to withdraw from the study for any reason. Also, the investigators may also request that a subject withdraw from the study or intervention be discontinued, for safety or other reasons. The criteria for intervention discontinuation or study withdrawal may include:

- (1) The subject's request;
- (2) Inability to participate due to relocation or other personal reasons;
- (3) Adverse events that require un-blinding or necessitate stopping the study drugs;
- (4) Seizures;
- (5) Persistent increase in elevated liver enzymes following study dose de-escalation or clinical or biochemical evidence of hepatic disease.

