9. STATISTICAL CONSIDERATIONS

9.1. GENERAL DESIGN

The study is a 2-arm double-blinded RCT. The statistical analysis will follow the intention-to-treat approach. Intention-to-treat (ITT) and per-protocol analyses will be performed.

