9.3. DATA ANALYSIS

Table 2 provides a list of main outcomes.

Table 2. Independent, main outcome and other variables to be used in the analyses	
Independent:	Group (Montelukast vs placebo)
Safety outcome:	GI symptoms (diarrhea, nausea, vomiting), anaphylaxis, elevated liver enzymes, PT/INR, behavioral changes, seizures, number of discontinuations from Montelukast, treatment-emergent AE/SAE, deaths
CSF outcomes:	CSF amyloid and tau, inflammatory proteins
Vascular outcomes:	PWV/PWA
Imaging outcomes:	Perfusion, hippocampal volume
Cognitive outcomes:	CDR, NIH Toolbox Cognition battery (NIHTB-CB)

Baseline characteristics including demographic, social and cognitive measures will be compared between the 2 groups to assess randomization fidelity. The list of the main variables is shown in Table 2. We will compare the change in our outcomes over the study period between the treatment and placebo arms using Mixed Models. For the dose response analysis, the dose vs cysLT-1 receptor activity will be plotted to explore the degree of cysteinyl leukotriene modulation at the various doses.

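### Section 7.4 does not clearly promise outcome follow-up to participants who stop study drug for an adverse event in about the first 22 weeks, which sits badly with intention-to-treat and with section 5.3.1

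*Combined protocol and SAP*

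**What the plan says.** Section 7.4 sets the follow-up rule after an adverse event: "If the event results in intervention discontinuation (>5 months) but not study withdrawal, the participant will be followed as defined in the study". The next sentence invites the participant to the final visit, "including all study procedures planned for that visit if the participant has been in the study for more than 5 months post-baseline evaluation". The second paragraph of 7.4 gives the physician several options ("The physician may discontinue the study medication immediately, elect to lower the dose of the study medication", among others) and adds: "The subject may continue in the study if on the lower dose of the study medication, they experience some resolution of symptoms". It does not say what happens to the visits of someone taken off drug altogether.

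For a different reason for stopping, clinical use of an LTRA or of a drug that may contraindicate one, section 5.3.1 is unconditional: such participants "will have their study medication discontinued but will continue to be in the study and have their subsequent visits and measures completed".

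Section 8 puts stopping drug and leaving the study under one list, introduced by "The criteria for intervention discontinuation or study withdrawal may include". Section 6.10.2 lists visits at 6 weeks and at 3, 6 and 12 months and does not mention participants off drug.

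On analysis, section 9.1 states "The statistical analysis will follow the intention-to-treat approach", with a per-protocol analysis as well. Section 9.3 states "We will compare the change in our outcomes over the study period between the treatment and placebo arms using Mixed Models".

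**The concern.** The bracket could mean that the stop happens more than five months into the study, or that the drug is off for more than five months. The sentence right after it counts five months from baseline, which makes the first meaning the more natural one. On that meaning, 7.4 makes no follow-up promise for adverse-event stops during dose escalation, after the six-week liver test, or at any other time in the first five months.

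An intention-to-treat comparison of change needs outcomes from participants who have stopped drug. Most of this trial's outcomes are measured late, so an early stopper who is let go leaves only baseline values, and these cannot be recovered at analysis. Safety laboratory data start at week 6, so safety is less exposed. The effect falls mainly on LTE4, the target-engagement measure that belongs to the primary objective, and on the secondary effect-size estimates.

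**Working it through.** **Timing.** One month = 365.25/12/7 = 4.348 weeks, so five months = 21.7 weeks and twelve months = 52.2 weeks.

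- Time-before-stop reading: stops before week 21.7 carry no follow-up promise.
- Length-of-stop reading: a permanent stop at week 10 leaves 52.2 − 10 = 42.2 weeks off drug, which is over five months, so it is covered.

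The two readings therefore give opposite answers for the same early stopper.

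**An early stop the plan itself foresees.** Section 5.1 checks liver enzymes at week 6, rechecks 2 weeks after a first dose reduction, and looks again 2 weeks after a second. Study drug can be stopped at the end of that sequence: 6 + 2 + 2 = week 10.

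**What that participant has by then (Table 1 and section 6.7).**

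| Measure | First repeat after baseline |
|---|---|
| Safety laboratory tests | week 6 |
| Cognitive battery, LTE4 | month 6 |
| CSF, MRI, PWV/PWA, functional battery | month 12 |

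A week-10 stopper who is not retained has no post-baseline value in the last two rows.

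**Does the final-visit sentence rescue early stoppers?** Its condition is time in the study. A week-10 stopper who is kept in the study meets it once past month 5. It excludes only those who were not kept, and the text does not say whether early stoppers are kept.

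**Illustrative size.** The plan gives no stop rates, SD or alpha. Assumptions:

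- 18 randomised per arm (36 in section 3, allocated 1:1);
- all 36 − 30 = 6 allowed losses arise by this route, except in the less balanced case below, which uses five;
- two-sided 5% test;
- stoppers do worse than completers by d, in SDs of change.

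Formulas: bias = (active stops/18 − placebo stops/18) × d; SE = √(1/n1 + 1/n2) among completers; rejection rate from the noncentral t with n1 + n2 − 2 degrees of freedom.

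| Losses, active v placebo | d (SD) | Bias toward drug (SD) | SE (SD) | Type I error |
|---|---|---|---|---|
| 3 v 3 | any | 0 | 0.365 | 5.0% |
| 4 v 2 | 0.5 | (2/18) × 0.5 = 0.056 | 0.366 | 5.2% |
| 4 v 2 | 1 | (2/18) × 1 = 0.111 | 0.366 | 6.0% |
| 4 v 1 | 1 | (3/18) × 1 = 0.167 | 0.361 | 7.3% |

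Losses of 2 v 4 give the same sizes as 4 v 2 with the opposite sign. If stoppers do not differ from completers, bias is zero. The 3 v 3 case leaves the planned 15 per group, so no precision is lost beyond plan.

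A mixed model does not remove this bias. In simulations of a maximum-likelihood model with baseline plus one follow-up, stoppers giving baseline only and a deficit unrelated to baseline, the bias was 0.11 SD for 4 v 2 and 0.17 SD for 4 v 1 (both at 1 SD), and 0.00 for 3 v 3. Results were the same at baseline–follow-up correlations of 0.5 and 0.8.

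**The case against.** The strongest reply is that silence is not loss. Section 7.4 itself separates stopping drug from withdrawing. Someone who has not withdrawn is still a participant, section 6.10.2 lists visits with no on-drug condition, and section 9.1 specifies intention-to-treat. No passage says that early stoppers are dropped, and every stop time is covered on at least one reading of the bracket. This stands as far as it goes: the plan may intend full follow-up. But 7.4 is the specific rule for adverse-event stops and it attaches a condition, so the general visit list does not settle the matter. Staff could read it either way for the same person.

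A reader might infer more: that follow-up is assured on both readings only for stops between about week 22 and week 30, which is 2 of 12 months (17%), and that late stoppers lose their month-12 measures. The documents do not support that. The week-30 limit (52.2 − 21.7 = 30.4) arises only if a permanent stop counts as short because the study ends. If a permanent stop simply counts as longer than five months, the readings agree from week 21.7 to week 52.2, which is 30.4 of 52.2 weeks (58%). A late stopper still in the study also meets the time-in-study condition for the full final visit.

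Nor should section 5.3.1 be read as contradicting 7.4. It covers a different reason for stopping, so this is an inconsistency of approach.

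Finally, nothing shows that bias would occur. Both arms are blinded under one rule, and section 2.2 reports similar adverse events on drug and placebo in other populations. That stands too.

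**Conclusion.** The point holds for early stops. Section 7.4 leaves it unclear whether participants who stop drug for an adverse event in about the first 22 weeks keep their month-6 and month-12 assessments, and its more natural reading makes them no such promise. That is at odds with the intention-to-treat comparison of change and with section 5.3.1; sections 6.10.2 and 8 do not resolve it.

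The bias figures only illustrate what could happen. They assume the stop counts, the deficit and the 5% level, and they assign every allowed loss in the six-loss cases to this route, although section 8 also lists personal request and relocation. In the 4 v 2 case the bias is at most 0.111/0.366 = 0.30 of a standard error. The reason to act is the unclear collection rule in a trial planned at 15 per group, where missed outcomes cannot be recovered. It is a cheap improvement worth making, and no demonstrated bias is claimed.

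**What to change.** Change data collection only.

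- In 7.4, remove the five-month condition on outcome collection. Participants whose study drug is stopped for any reason, at any time, are asked to complete the scheduled 6- and 12-month assessments unless they withdraw or are withdrawn from the study.
- Reconcile both paragraphs of 7.4, and section 8, with 5.3.1 and 9.1 by distinguishing stopping study drug from leaving the study. No dose, stopping rule or investigator discretion changes.
- Report missing month-6 and month-12 data by arm and by reason.

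This goes a little beyond defining the bracket. A definition alone could still leave early stoppers without outcomes.

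The cost is amendment wording and a few off-drug visits. Some participants will still decline the lumbar puncture or MRI, so some of those data will remain missing.

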7.5. INCIDENTAL FINDINGS

Incidental findings (lab testing, neuroimaging or vascular testing) identified during the conduct of the study that do not require immediate medical care will be reported to the subject with instructions to seek medical care from the participant's healthcare provider. Those with incidental findings requiring urgent care will be referred to an emergency room in a facility of their choosing.

8. INTERVENTION DISCONTINUATION AND STUDY WITHDRAWAL

A subject may choose to withdraw from the study for any reason. Also, the investigators may also request that a subject withdraw from the study or intervention be discontinued, for safety or other reasons. The criteria for intervention discontinuation or study withdrawal may include:

- (1) The subject's request;
- (2) Inability to participate due to relocation or other personal reasons;
- (3) Adverse events that require un-blinding or necessitate stopping the study drugs;
- (4) Seizures;
- (5) Persistent increase in elevated liver enzymes following study dose de-escalation or clinical or biochemical evidence of hepatic disease.

9. STATISTICAL CONSIDERATIONS

9.1. GENERAL DESIGN

The study is a 2-arm double-blinded RCT. The statistical analysis will follow the intention-to-treat approach. Intention-to-treat (ITT) and per-protocol analyses will be performed.

9.2. RANDOMIZATION

The study blinded biostatistician will provide oversight of randomization fidelity and blinding. Randomization will be stratified by **use of cholinesterase inhibitors or Memantine (yes vs no)** and by **cognitive group** (MCI vs early AD) using a computerized random number generator (SAS, V9.4). Only the pharmacy will have access to the randomization lists. As the pharmacist is notified that an individual subject is eligible for randomization, the pharmacist prepares the appropriate blinded study product. The pharmacist will enter the subject ID, date of product randomization, and the unique allocation sequence number on a web-based data form.

9.3. DATA ANALYSIS

Table 2 provides a list of main outcomes.

Table 2. Independent, main outcome and other variables to be used in the analyses	
Independent:	Group (Montelukast vs placebo)
Safety outcome:	GI symptoms (diarrhea, nausea, vomiting), anaphylaxis, elevated liver enzymes, PT/INR, behavioral changes, seizures, number of discontinuations from Montelukast, treatment-emergent AE/SAE, deaths
CSF outcomes:	CSF amyloid and tau, inflammatory proteins
Vascular outcomes:	PWV/PWA
Imaging outcomes:	Perfusion, hippocampal volume
Cognitive outcomes:	CDR, NIH Toolbox Cognition battery (NIHTB-CB)

Baseline characteristics including demographic, social and cognitive measures will be compared between the 2 groups to assess randomization fidelity. The list of the main variables is shown in Table 2. We will compare the change in our outcomes over the study period between the treatment and placebo arms using Mixed Models. For the dose response analysis, the dose vs cysLT-1 receptor activity will be plotted to explore the degree of cysteinyl leukotriene modulation at the various doses.

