3. STUDY DESIGN

This is a **PHASE II**, 1-year double-blind placebo-controlled randomized clinical trial where participants will be treated with Montelukast (escalating doses: 10, 20 to 40 mg) or matched placebo. The study will enroll 36 participants to account for an expected 20% drop-out rate in order to achieve a sample size of 30 with 15 participants in each group.

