6.7. LEUKOTRIENE INHIBITION ACTIVITY

Cysteinyl leukotrienes (LTE₄) and CysLT type-1 (CysLT1) receptor activity will be assessed via single blood or urine sampling at baseline, 6 and 12 month visits by a highly selective and sensitive Liquid Chromatography/Tandem Mass Spectrometry (LC/MS/MS) method described previously.^{78,79} We will use this as a measure to assess the degree of blockade of CysLT type-1 (CysLT1) receptor activity.

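### Randomisation is stratified on two factors, but section 9.3 and Table 2 name only treatment group and do not say how baseline enters the mixed models

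*Combined protocol and SAP*

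**What the plan says.** - **Section 9.2** stratifies by "use of cholinesterase inhibitors or Memantine (yes vs no") and by cognitive group (MCI or early AD), "using a computerized random number generator (SAS, V9.4"). It does not say whether allocation is blocked within the four strata.
- **Section 9.3** gives the model in one sentence: "We will compare the change in our outcomes over the study period between the treatment and placebo arms using Mixed Models". It lists no fixed effects, baseline term or visit structure. Baseline data are mentioned only for a between-arm comparison to check the randomisation.
- **Table 2** is titled "Independent, main outcome and other variables to be used in the analyses". Its only independent variable is "Group (Montelukast vs placebo"), and no row lists a covariate.
- **Section 9.1** states: "The statistical analysis will follow the intention-to-treat approach". A per-protocol analysis is added.
- **Section 3** enrols 36 participants "to account for an expected 20% drop-out rate in order to achieve a sample size of 30 with 15 participants in each group".
- **Table 1** schedules CSF, MRI and PWV/PWA at baseline and month 12 only. The cognitive battery and LTE4 are at baseline, 6 and 12 months.
- **Section 6.7** says that leukotriene activity "will be assessed via single blood or urine sampling at baseline, 6 and 12 month visits". LTE4 is not in Table 2, and 9.3 plans only a plot of receptor activity against dose.

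**The concern.** The secondary objective in section 1 is to estimate effect sizes from about 15 participants per arm, so the width of the interval largely decides how useful each estimate is. The sponsor judged two factors important enough to stratify on and collects a baseline value for every efficacy outcome, yet the plan commits to using none of this in the model.

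The term Mixed Models does not settle the matter. The sentence in 9.3 allows at least three readings: a change score as response, the follow-up value with baseline as covariate, or baseline as one of the repeated responses. The choice between them stays open until data are seen. At stake are precision, a calibrated test and a model fixed in advance.

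**Working it through.** **The plan's own figure.** 30 × 1.2 = 36 reproduces the enrolment. (36 × 0.8 = 28.8, so 30 is slightly rounded up; the point does not depend on this.) The plan gives no figure for precision.

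**Step 1: does a mixed model recover precision by itself?** With baseline as a response, free arm means at baseline and complete data, the treatment × time estimate is

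(mean at 12 − mean at 0, montelukast) − (mean at 12 − mean at 0, placebo),

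which is the group-only difference in change. For CSF, MRI and PWV/PWA a change score leaves one value per participant, with nothing repeated to model. So the text permits a group-only comparison.

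**Step 2: cost of the extra terms.** Treatment alone leaves 30 − 2 = 28 residual degrees of freedom. Adding two factors and baseline leaves 30 − 5 = 25. Assumptions for the simulation: change has variance 1, both factors are binary at 50%, and allocation is either in blocks of 4 within strata or simple. Mean 95% half-width when the added terms explain nothing:

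| n | Allocation | Group only | Adjusted | Ratio |
|---|---|---|---|---|
| 30 | blocked | 0.744 | 0.766 | 1.03 |
| 30 | unblocked | 0.755 | 0.802 | 1.06 |
| 20 | blocked | 0.929 | 0.982 | 1.06 |
| 20 | unblocked | 0.951 | 1.058 | 1.11 |

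n = 20 is an assumed CSF or MRI subset; section 4.2, item 11, admits people who can have only one of the two procedures.

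**Step 3: break-even.** If the terms jointly explain a share R² of the variance in change, the interval ratio is about (ratio above) × √(1 − R²). Setting this to 1 gives R² = 1 − 1/ratio². At n = 30 that is about 6% blocked and 12% unblocked. At n = 20 it is about 10% and 19%.

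| Joint R², n = 30 | Blocked | Unblocked |
|---|---|---|
| 0 | 3% wider | 6% wider |
| 0.15 | 5% narrower | 2% narrower |
| 0.25 | 11% narrower | 8% narrower |
| 0.40 | 20% narrower | 18% narrower |

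**Step 4: in terms of correlation.** With equal variances at both times and correlation r, baseline explains (1 − r)/2 of the variance in change: 25%, 15% and 5% at r = 0.5, 0.7 and 0.9. Extremes over r from 0.5 to 0.9 and strata R² from 0 to 0.3:

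- r = 0.9, strata R² 0, unblocked: 0.753 → 0.781, about 4% wider.
- r = 0.5, strata R² 0.3, blocked: 0.749 → 0.556, about 26% narrower.

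**Step 5: precision or calibration?** In the 26% case the sampling SD of the estimate falls only from 0.309 to 0.271, about 12%. Blocking has already removed most between-stratum variation from the estimate, but the group-only standard error does not know it. The rest of the narrowing corrects an over-wide interval. A separate simulation, with allocation balanced exactly within strata and adjustment for strata only (n = 30, two-sided 5% level), shows the same effect:

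| Strata R² | Type I error, group only | Power at 1.0 SD: group only → with strata |
|---|---|---|
| 0 | 0.050 | 0.76 → 0.76 |
| 0.1 | 0.038 | 0.76 → 0.80 |
| 0.2 | 0.031 | 0.77 → 0.84 |
| 0.3 | 0.020 | 0.79 → 0.88 |

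Type I error with strata in the model is about 0.05 throughout. Without blocking, the group-only test also stays near 5%.

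**Step 6: how the strata must enter if baseline is a response.** A stratum main effect shifts baseline and month 12 equally and cancels out of the change. Simulated at strata R² 0.3 and r = 0.7, a constrained-baseline model with main effects only differs from ANCOVA by 0.06 on average (blocked) or about 0.15 (unblocked), with change SD about 1. With factor × visit terms it matches ANCOVA exactly.

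**The case against.** The plan contradicts nothing here. Section 9.3 presents Table 2 as the main variables, not all of them, and a mixed model can hold every term requested. Efficacy and effect size are secondary objectives in a 30-participant trial. Adjustment can also lose: at r = 0.9 baseline explains 5% of change, below every break-even above, and at n = 20 unblocked even r = 0.7 (15%) falls short of 19% if the strata explain nothing. Cognitive group is partly defined by the CDR memory box (section 4.1), so entering it beside baseline cognition adds less for those outcomes. All of this stands. It limits the size and urgency of the point, but does not tell the analyst which model to fit.

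Four stronger readings are tempting and are not supported:

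- *The plan excludes the strata.* It leaves them unstated.
- *Omitting them biases the estimate or inflates type I error.* It does neither; under blocking the error is in the conservative direction.
- *The group-only analysis is usually less precise.* The documents contain nothing from which to judge how often the break-even is passed.
- *Modelling baseline as a response rescues participants without a baseline.* Section 6.10.2 randomises after baseline data are collected, so that pattern should be uncommon. Those missing only month 12 add little to the contrast.

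**Conclusion.** The gap is real and worth closing, as an improvement to the analysis rather than the correction of an error. As written, a group-only comparison of change complies with the plan. It is valid, but gives a wider interval than the adjusted analysis once the factors and baseline together explain more than about 6% (blocked) or 12% (unblocked) of the variance in change at n = 30. It is also conservative if allocation is blocked within prognostic strata.

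The range from about 4% wider to about 26% narrower is illustrative. It rests on assumed correlations, strata effects, factor prevalences and block size, none of which the documents give. The upper end should not be read as a pure gain in precision, since about half of it is calibration. The scope is the continuous efficacy, biomarker and LTE4 outcomes, not the safety events in Table 2.

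**What to change.** In 9.3, with a covariate row in Table 2, state that continuous efficacy, biomarker and LTE4 outcomes are analysed with treatment, the baseline value and the two stratification factors, and that the adjusted difference is reported with its 95% CI. Omit a factor-by-factor interaction, since four cells average only 30/4 = 7.5 participants.

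- **Baseline and month 12 only (CSF, MRI, PWV/PWA):** ANCOVA on the month-12 value with baseline and both factors.
- **Months 6 and 12 (cognitive battery, LTE4):** mixed model with baseline as covariate, both factors, visit, treatment × visit and a small-sample degrees-of-freedom correction such as Kenward-Roger. Add LTE4 to Table 2; the dose plot can stay.
- **If baseline is instead modelled as a response** with arm means constrained equal at baseline, include factor × visit terms, because main effects alone do not adjust the change.

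In 9.2, state whether allocation is blocked within strata.

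The cost is a paragraph, a table row and a sentence, with no new data. Statistically it is 3 residual degrees of freedom and, if the terms explain nothing, an interval about 3 to 6% wider at n = 30 or 6 to 11% wider at an assumed n = 20. The change does not recover participants with no measurement of an outcome and should not be presented as a remedy for missing data.
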